SPANIK-HF Study

**SPANISH MULTICENTRIC STUDY OF HYPERKALAEMIA PREVALENCE, INCIDENCE AND
PROGNOSIS IN PATIENTS WITH HEART FAILURE AND REDUCED EJECTION FRACTION**

[Tracking code: ESR-17-13244]

ClinicalTrials.gov ID: NCT04141800

V2-18.02.2019

SUMMARY	4
1. BACKGROUND AND RATIONALE	7
2. GOALS	9
2.1. Main goal	9
2.2. Specific goals	9
3. STUDY DESIGN	10
3. 1. Definition of the study population and selection criteria	10
3. 2. Considerations about sample size	11
3. 3. Selection of centres	11
3. 4. Source of information	12
3. 5. Variables and CRF (appendix 1)	12
3. 6. Study development	13
3. 7. Limitations	13
4. DEFINITION OF VARIABLES OF INTEREST	14
5. DATA COLLECTION AND MANAGEMENT	16
5. 1. Data collection	16
5. 2. Data management	16
5. 3. Quality assurance	16
6. PLAN FOR DATA ANALYSIS	17
7. ETHICAL AND SECURITY ISSUES	18
Interference with the prescription habits of the attending physician	
Control and report of adverse reactions	
A.- Definitions	
B.- Recording of adverse events	
C.- Sponsor responsibility for report of SUSARs	

8. PRACTICAL ISSUES	22
8. 1. Working plan and chronogram	22
8. 2. Baseline and final reports	22
8. 3. Dissemination of results	23
8.4 Organisation of the study	23

SUMMARY

1. Promoter

Sociedad Española de Cardiología

2. Title of the study

SPANISH MULTICENTRIC STUDY OF HYPERKALAEMIA PREVALENCE, INCIDENCE AND PROGNOSIS IN PATIENTS WITH HEART FAILURE AND REDUCED EJECTION FRACTION

3. Main Researchers

[name] [name], A Coruña.

[name], Madrid.

[name] [name], A Coruña

4. Scientific Committee

[name], Valencia

[name], Córdoba

[name] [name], A Coruña.

[name], Madrid.

[name] [name], Asturias

[name], Barcelona

[name] [name]. Instituto Universitario de Ciencias de la Salud, Universidade da Coruña. A Coruña

[name], Barcelona

[name], Madrid

[name] [name], AISEC, Madrid

5. Participant centres and researchers

20 National Public Health System hospitals. Cardiology specialist physicians

6. Clinical Research Ethics Committee (CREC)

Hospital 12 de Octubre, Madrid

7. Main goal

To estimate prevalence and, in medium term basis (12 months), incidence of hyperkalaemia in heart failure (HF) outpatients with reduced ejection fraction (REF) and its relationship with non-optimal HF therapy and clinical outcomes (mortality and hospital admission).

8. Specific goals

- a. –Estimating Hyperkalaemia prevalence in these patients.
- b. -Assessing the role of hyperkalaemia with the use of non-optimal therapy doses.
- c. –Estimating 12 months hyperkalaemia incidence on these patients and describing the severity of the episodes.
- d. -Estimating incidence of HF hospital admission and/or death in these patients on a medium term basis (12 months) and its association with existence of hyperkalaemia during follow up.
- e. –Assessing hyperkalaemia risk during follow-up in relation with the existence of diabetes and/or renal failure (RF) at baseline visit.

9. Study design

National multicentric prospective observational study that includes 12 months follow-up of consecutive cases of HF outpatients with REF. Inclusion baseline visit and follow-up visits at 12 months will be scheduled for collecting clinical and blood sample data of patients.

10. Study population

The expected number of patients recruited in 20 Spanish research centres is 600.

11. Chronogram

Preparation of documentation and protocol: October 31st 2018

Identification and selection of coordinators and researchers: October 2018

Submission to “Agencia Española del Medicamento y Productos Sanitarios” (AEMPS):

November 2018

Presentation to Clinical Research Ethics Committees: November 2018

Contract signature: December 2018

Design of case report form (CRF) and electronic case report form (eCRF): January-March 2019

Dispatch to centres for assessment and approval: January-February 2019

Inclusion date for first patient: April 2019

Inclusion period: April 2019 – October 2019

Intermediate analysis and presentation of results: second semester 2019

End of 12 months follow up of the last patient: October 2020

Final analysis and presentation of definitive results: second semester 2020

12. Promoter and Coordinator Centre data

Promoter:

Sociedad Española de Cardiología

[name]

[name]

[contact]

[contact]

Coordinating Centre:

ODDS, S.L.

[name]

[name]

[contact]

[contact]

[contact]

www.oddsconsultores.es

1. BACKGROUND AND RATIONALE

In the last years, multiple reasons have been increasing the disease burden of heart failure (HF) in industrialised countries – also Spain –, being a very important health problem. It is foreseeable that this burden will continue increasing in our country¹.

In parallel with this evolution, several treatments already included in clinical practice guidelines^{2, 3}, have proved to be effective in selected groups of patients, especially those with systolic function impairment.

These treatments that interfere with the renin-angiotensin-aldosterone system, increase hyperkalaemia risk in HF patients as much as three times^{3, 4}. Hyperkalaemia is associated with conduction disorders and risk of potentially life-threatening arrhythmias; it is not rare at all, as 20 years ago estimations already indicated 1-10% prevalence in hospitalised patients⁵. More recent data among ACEI new users suggest in the first year 5,6% and 1,7% for potassium values >5 and >5,5 respectively.⁶ HF patients are at increased risk of hyperkalaemia, not only due to the drugs they receive (ACEIs/ARB-II, mineralocorticoids receptor antagonists (MRAs) and, more recently, sacubitril/valsartan), but also because of the frequent presence of comorbidities (diabetes or renal failure, among others).⁷

These drugs blocking the renin-angiotensin-aldosterone system have an IA indication in the clinical practice guidelines for patients with reduced ejection fraction, so their use is becoming more frequent and, subsequently, hyperkalaemia is a growing concern for treating HF patients.⁷

Despite the above mentioned, there is no evidence of prospective information for the estimation of hyperkalaemia problem in HF patients in the daily Spanish clinical practice, although some current registries allows an initial estimation of its prevalence. In a recent analysis of the patients included in Spain in the Heart Failure Registry of the European Society of Cardiology (ESC)⁸ 26,3% of patients (401/1526) where MRAs are indicated (REF), but not prescribed, the underlying reason for not prescription is Hyperkalaemia in 8,5% of them (34/401). There are many “not-prescriptions” that are not adequately justified, therefore hyperkalaemia has a larger prevalence (30,6%, 34/111) among cases where a cause for avoiding MRAs does exist. At least as important is the fact that the vast majority of patients, up to 3 of 4, do not reach the

2. GOALS

2.1. Main goal

To estimate prevalence and, in medium term basis (12 months), incidence of hyperkalaemia in heart failure (HF) outpatients with reduced ejection fraction (REF) and its relationship with non-optimal HF therapy and clinical outcomes (mortality and hospital admission).

2.2. Specific goals

- a. - Estimating Hyperkalaemia prevalence in these patients.
- b. - Assessing the role of hyperkalaemia with the use of non-optimal therapy doses.
- c. - Estimating 12 months hyperkalaemia incidence on these patients and describing the severity of the episodes.
- d. - Estimating incidence of HF hospital admission and/or death in these patients on a medium term basis (12 months) and its association with existence of hyperkalaemia during follow up.
- e. - Assessing hyperkalaemia risk during follow-up in relation with the existence of diabetes and/or renal failure (RF) at baseline visit.

3. STUDY DESIGN

National multicentric prospective observational study that includes 12 months follow-up of consecutive cases of HF outpatients with REF. Inclusion baseline visit and follow-up visit at 12 months will be scheduled for collecting clinical and blood sample data of patients indicated later on in this protocol.

The study will be performed in ordinary conditions of clinical practice; no additional procedures or interventions will be performed. Patients will be selected in cardiology outpatient clinics of 20 Spanish centres, including the first 30 patients meeting inclusion and exclusion criteria. All patients will undergo the common studies according to usual clinical practice and at least both, potassium and renal creatinine clearance values will be collected.

To respond to the main objective, prevalence of hyperkalaemia (as defined later in the protocol) at baseline will be determined as well as the appearance of new hyperkalaemia cases in the follow up of patients that had normal potassium levels at baseline visit; their relationship with outcomes of interest will also be determined.

Variables to be collected at each visit are indicated in appendix 1.

3. 1. Definition of the study population and selection criteria

The study population is composed of HF outpatients with REF from excellence Spanish centres.

The study will be performed in 20 Spanish centres, either SEC HF- excellence certified, integrating official research networks or with excellent performance proven in previous similar initiatives (relation of centres and researchers in Appendix 2).

Every centre will include the first 30 consecutive cardiology outpatients who fulfil the inclusion criteria and that do not present any exclusion criteria. All pre-screened patients will be indicated, together with the reason of their exemption if occurs.

Inclusion criteria

1. Patients, women or men, aged 18 or more
2. Documented HF with REF (<40%) diagnosis
3. Signed written informed consent

Exclusion criteria

1. Any type of disorder affecting the capacity to give free and informed written consent
2. Clinical trial enrolment at the moment of the inclusion
3. Patients suffering stage 5 chronic kidney disease
4. Patients with less than a year life span due to diseases different from HF
5. Not having completed HF drug titration stage at the moment of inclusion (this stage is not completed if, on doctor's judgement, possible maximum doses have not been reached in RAA system drugs and any of these drugs has been included or dose-modified in recruitment visit)
6. Informed consent refusal

At any time during follow-up patients can leave the study (and will be censored in the analysis) or retire their consent (and will be excluded from the analysis).

3. 2. Considerations about simple size

Assuming a 10% risk of outcomes (mortality or HF hospital admission) among the exposed (hyperkalaemia), 2.5% among the non-exposed and a 7:1 non-exposed/exposed ratio, 73 exposed and 511 non-exposed patients should be included to have a 80% power to detect these differences with a 95% confidence level. The recruitment goal is set at 600 patients.

This sample size allows a precision of $\pm 2,4\%$, assuming a prevalence of hyperkalaemia at baseline of 10% and with a 95% confidence level. Furthermore, assuming 5% hyperkalaemia cumulative incidence through follow-up among hyperkalaemia-free patients at baseline, the proposed sample size, allows a precision of $\pm 1,8\%$ with a 95% confidence level.

3. 3. Selection of centres

The number of participant centres throughout Spain will be 20 and a cardiologist will be the principal investigator at every centre. The centres have been selected either among those with excellence-certified HF units, included in CiberCV Consortium or

with good performance in previous similar registries; this selection is not random, but based on interest and high performance criteria in the field of HF.

3. 4.- Source of information

Data will be obtained directly from the participants at the planned visits and completed with the review of their medical records if needed.

3. 5. Variables and CRF (appendix 1)

The main outcome variables are:

a.- Hyperkalaemia. Serum Potassium (K^+) will be measured in baseline and follow-up visits, but also if there is any intermediate hospital admission. All available potassium measurements during follow-up will be reviewed and values of hyperkalaemia identified. Hyperkalaemia will be considered with (K^+) Values $> 5,4$ mEq/L

b.- Proportion of patients using drugs with proven efficacy for HF with REF -but also linked with hyperkalaemia- (ACEIs/ARB-II/ARNI and MRAs) and proportion of patients with use of optimal doses (based on current ESC heart failure guidelines²) of the same drugs; reason for not using them (or not receiving optimal doses) will be registered.

Proportion of patients in the following categories will also be computed:

- No ACEi/ARB/ARNI or at less than target dose and no MRA
- ACEi/ARB/ARNI at target dose and no MRA
- ACEi/ARB/ARNI at target dose and MRA at less than target dose
- ACEi/ARB/ARNI at target dose and MRA at target dose

c.- Hospital admissions during follow-up and main cause for them. Outcomes considered will include HF admissions caused by hyperkalaemia and related events. Outcome Serum (K^+) values will be also registered.

d.- Mortality and cause.

HF (and hyperkalaemia) hospital admissions and mortality will be independently considered as outcomes; joint outcome incidence of both will be also calculated.

The remaining variables are set out in appendix 1. The most important variables are defined in section 4.

3. 6. Study development

Every participating centre will include from inclusion date (as described in section 3.1) the first 30 heart failure outpatients who fulfil the inclusion criteria and none of the exclusion ones. The excluded patients will be also registered, pointing out the reason of exclusion. The data to be collected during the initial visit will include the variables described in Appendix 1: demographic, clinical, blood sample test, and functional. A follow-up and final visit will be scheduled after 12 months for collecting all the variables the study requires (Appendix 1). Hospitalisation data since inclusion visit will be also collected, together with the information of blood sample test performed in such period for detecting hyperkalaemia episodes. Mortality data will include date and cause, where possible. If follow-up visit cannot be conducted, the reason for it will be registered. The collection and management of data is described in section 5. The envisaged length of the study is 24 months since approval date.

3. 7. Limitations

Mild elevations of serum potassium that do not lead to hospital admission between planned visits may go unnoticed.

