4. DEFINITION OF VARIABLES OF INTEREST

Heart Failure (HF) with reduced ejection fraction (REF): Patients with confirmed diagnosis of HF and with ejection fraction <40%.

Hyperkalaemia: K^+ values > 5,4 mEq/L.

Optimal doses: the maximum doses of renin-angiotensin-aldosterone related drugs that, according to the physician's judgement, the patient can receive. If any of these drugs (ACIEs, ARB-II, MRAs or sacubitril-valsartan) is *de novo* introduced at the initial visit, optimal doses will be not considered established.

A previous personal history of diseases and/or outcomes will be registered according to the usual practice of every centre. Some of the clarifications needed in every case are indicated as follows:

- **Coronary artery disease.** Documented existence of any of the following: acute myocardial infarction (AMI), acute coronary syndrome (ACS), coronary revascularisation (Percutaneous Coronary Angioplasty –PCA - or CABG) or coronary stenosis > 50% of arterial lumen in imaging test.
- **Cerebrovascular diseases.** History of ischaemic/haemorrhagic stroke or carotid stenosis > 50% of arterial lumen in imaging test.
- **Peripheral artery disease.** Aneurysm of thoracic/abdominal aorta or lower limb peripheral arterial disease.
- **Death due to a major cardiovascular event.** Due to ACS, HF, arrhythmia (sudden death), arterial aneurysm rupture or stroke.
- **Arterial thromboembolism.** Embolism phenomenon affecting arterial territory – (except pulmonary territory).
- **Ischaemic stroke.** Focal neurological deficit originated by cerebral ischemia; persists more than 24 hours after a sudden onset.

- **Haemorrhagic stroke:** Focal neurological deficit with sudden onset and originated by intracranial haemorrhage.
- **Acute coronary syndrome (ACS):** Acute coronary event that present typical ECG alterations and/or enzyme elevation.
- **NYHA functional class:**

Functional class I	No limitation. Ordinary physical activity does not cause dyspnoea, fatigue or palpitations.
Functional class II	Light limitation of physical activity. Everyday activities cause dyspnoea, fatigue or palpitations
Functional class III	Moderate limitation of physical activity. Activities considered less intense that everyday ones cause dyspnoea, fatigue or palpitations. Patient, however, does not present resting dyspnoea.
Functional class IV	Inability to perform activities without limitations. Symptoms may be present even at rest

- **Anaemia**

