6. PLAN FOR DATA ANALYSIS

Hyperkalaemia prevalence at basal visit and the rate of patients who do not receive and/or reach optimal doses of drugs of interest (ACIEs, ARB-II, MRAs) will be estimated and their corresponding 95% confidence intervals computed. The reason for not receiving and/or reaching optimal doses of drugs will be described, especially if it is due to hyperkalaemia.

For those patients who do not present hyperkalaemia at baseline, 12 month hyperkalaemia cumulative incidence (95% confidence interval) will be estimated; also it will be estimated the proportion of patients who have to modify their therapy due to hyperkalaemia.

The number of episodes of hyperkalaemia during follow-up in relation to the number of patients will be estimated and their severity and the therapy changes that induced described. Also 12 months cumulative incidence of clinical outcomes will be estimated: hospitalisation due to HF or to, hyperkalaemia (and related events) and mortality, considered as individual and composite outcomes. The association between hyperkalaemia and occurrence of outcomes will be analysed and also adjusted using potential confounding factors by means of logistic regression models

The quantitative variables will be generally described using either the mean and the standard deviation or the median and interquartile range according them following or not a normal distribution. When comparing groups, t-student test will be used for continuous variables and chi-square test for qualitative ones.

Both, intermediate and final analysis, are planned to be carried out after baseline-visit closure and at the end of follow up (12 months).

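### Exclusion criterion 5 counts a dose change in any direction, so a patient below the possible maximum whose RAA drug is cut for potassium at the recruitment visit can drop out of the baseline prevalence

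*Protocol*

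**What the plan says.** Protocol section 3.1, exclusion criterion 5, is headed by its purpose: "Not having completed HF drug titration stage at the moment of inclusion". It then defines an unfinished titration by two conditions joined by *and*. The first is that, as the doctor sees it, the highest achievable RAA doses are not yet in place. The second is that "any of these drugs has been included or dose-modified in recruitment visit". This second condition gives neither a direction nor a reason for the dose change.

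The outcome is measured at the same visit. Section 3 states that "prevalence of hyperkalaemia (as defined later in the protocol) at baseline will be determined", section 3.5 says that potassium "will be measured in baseline and follow-up visits, but also if there is any intermediate hospital admission", and section 4 sets the threshold at "K^+ values > 5,4 mEq/L". Section 6 plans to estimate "Hyperkalaemia prevalence at basal visit" with a 95% confidence interval.

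Section 4 defines optimal doses as the most the patient can receive in the physician's judgement. It adds that if an RAA drug is newly "introduced at the initial visit, optimal doses will be not considered established". It does not mention a dose modification.

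Sections 3.1 and 3.6 provide for registering excluded patients with the reason. Section 3.7 (Limitations) mentions only mild potassium rises between visits that may go unnoticed.

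**The concern.** The criterion is meant to keep out patients whose treatment is still being built up. Its second condition is wider than that purpose, because a reduction or a stop is also a dose modification. When such a change is a reaction to a high potassium found at the recruitment visit, eligibility depends on the very quantity that goal a sets out to estimate.

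The patients at risk of being lost are those the study most wants to count: hyperkalaemic at baseline, with therapy limited by potassium. Losing them would lower the baseline prevalence. It could also weaken the picture for goal b, which looks at hyperkalaemia and non-optimal doses. Each centre takes the first 30 eligible patients, so an excluded patient is replaced by the next one. The total stays at the planned 600 and the confidence interval gives no sign of the loss.

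**Working it through.** **1. Does the rule as written exclude such a patient?** Take three patients whose RAA drug is reduced at the recruitment visit because of that visit's potassium.

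- Judged to have already reached the possible maximum: the first condition fails and the patient stays eligible.
- Judged below the possible maximum, for instance on one RAA drug while another is cut: both conditions are met and the patient is excluded.
- Potassium result not available until after the visit: the change is not made at the visit, the second condition fails and the patient stays eligible.

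So the exclusion arises in the second case only, but there it follows from the literal wording.

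**2. The plan's own precision.** Inputs from section 3.2: prevalence 10%, 600 patients, 95% confidence.

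Half-width = 1.96 × √(0.10 × 0.90 / 600) = 0.0240, or ±2.4 points. The stated figure is reproduced.

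**3. Sensitivity of the prevalence.** Let *p* be the true prevalence among patients the study means to include. Let *f* and *g* be the shares of hyperkalaemic and non-hyperkalaemic patients among them that criterion 5 removes. Then

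observed prevalence = p(1 − f) / [p(1 − f) + (1 − p)(1 − g)].

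The value *p* = 10% is the plan's assumption. The documents give neither *f* nor *g*, so both are assumptions shown over a range.

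| f | g | Calculation | Observed | Bias (points) |
|---|---|---|---|---|
| 10% | 0 | 0.090 / 0.990 | 9.1% | −0.9 |
| 25% | 0 | 0.075 / 0.975 | 7.7% | −2.3 |
| 50% | 0 | 0.050 / 0.950 | 5.3% | −4.7 |
| 10% | 10% | 0.090 / 0.900 | 10.0% | 0 |
| 25% | 10% | 0.075 / 0.885 | 8.5% | −1.5 |
| 50% | 10% | 0.050 / 0.860 | 5.8% | −4.2 |
| 0 | 10% | 0.100 / 0.910 | 11.0% | +1.0 |

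**4. Where the bias equals the planned precision.** With *g* = 0, set the observed prevalence to 10% − 2.4% = 7.6%:

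f = 1 − (0.076 × 0.90) / (0.10 × 0.924) = 1 − 0.0684 / 0.0924 = 0.26.

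About 26% of hyperkalaemic candidates would have to be lost. Any exclusion of non-hyperkalaemic patients for dose changes made for other reasons moves that point higher.

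**The case against.** The strongest reply is that the two conditions apply jointly. A reader who sees only the second might infer that any patient with a dose change at the visit is removed. That is not the rule. A patient whose dose is cut for potassium can readily be judged to have reached what is possible and then stays in. A doctor who still sees room to increase may fairly call the titration unfinished. This stands, and it limits the concern to the subgroup judged below the maximum. It does not remove the concern, because nothing tells a centre how to classify a reduction made for potassium.

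The mechanism also needs the potassium result to be known and acted on at the visit, and the protocol does not fix that timing. This stands too.

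A third reply is that the criterion also removes normokalaemic patients, which pushes prevalence up. Patients with normal potassium who are still being up-titrated are outside the intended population, so leaving them out defines the target and does not bias it. Dose changes for other reasons in patients within the target do offset the loss, as the rows with *g* = 10% show. The direction is downward only when *f* exceeds *g*.

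Three stronger readings are tempting and not supported:

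- That section 4 contradicts criterion 5. Section 4 names a new drug as one case in which optimal doses are not established; it does not say this is the only case. The two triggers differ, but both can be followed.
- That goal d loses exposed patients. Goal d is tied to hyperkalaemia during follow-up, not to baseline cases.
- That the effect must be large because section 1 reports up to 3 in 4 patients below the goal dose of mineralocorticoid receptor antagonists. That figure concerns goal doses in another registry, not the doctor's judgement of what is possible for a given patient. It supplies no value for *f*.

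**Conclusion.** The concern holds as a fault of wording with a possible effect on goal a. Criterion 5 as written can exclude a patient judged below the possible maximum because an RAA drug was reduced or stopped in response to the potassium measured at that visit. That is broader than the stated aim of removing unfinished titration, and it makes eligibility partly dependent on the outcome.

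A bias is possible, not demonstrated. It depends on the doctor's judgement on the first condition, on the result being known at the visit, and on hyperkalaemic patients being lost more often than others. The figures of 9.1%, 7.7% and 5.3% illustrate losses of 10%, 25% and 50% with a true prevalence of 10% and no other exclusions; none of these fractions can be estimated from the documents. The bias would match the planned ±2.4 points at a loss of about 26%, and it would be smaller if other dose changes also removed non-hyperkalaemic patients. A larger sample would not reduce it.

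**What to change.** In section 3.1, for eligibility only, limit the second condition of criterion 5 to an RAA drug newly started or increased at the recruitment visit. State that a reduction or a stop at that visit does not by itself exclude the patient. Reconcile this wording with the section 4 statement on when optimal doses are not established, so that all 20 centres work from one description.

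Report the number excluded under criterion 5, taken from the register of excluded patients already planned. Adding potassium values to that register would allow a tighter bound, but it means holding clinical data on people who may not have consented, so it is not proposed as a routine step.

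The cost is one phrase in the eligibility criteria, a matching edit in section 4 and one line in the report. Nothing changes in patient care, and no view is taken on any dose decision. The downside is that a few patients with a dose reduction at the recruitment visit enter the cohort.

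### Section 3.1 censors patients who leave, but the logistic regression that Section 6 names for the hyperkalaemia-outcome association cannot use a censored patient unless it is weighted

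*Protocol*

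**What the plan says.** Protocol Section 3.1 sets the rule for incomplete follow-up: "patients can leave the study (and will be censored in the analysis) or retire their consent (and will be excluded from the analysis". Patients who withdraw consent fall under a separate rule of exclusion.

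Section 6 (Plan for data analysis) says that the association between hyperkalaemia and the clinical outcomes will be analysed and also "adjusted using potential confounding factors by means of logistic regression models". Group comparisons use the t-test and the chi-square test. Section 6 names no method based on follow-up time.

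For incidence, Section 6 states a quantity but no estimator: "For those patients who do not present hyperkalaemia at baseline, 12 month hyperkalaemia cumulative incidence (95% confidence interval) will be estimated". The clinical outcomes are treated the same way.

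Section 2.2, goal d, takes hyperkalaemia arising during follow-up as the exposure and HF admission and/or death over 12 months as the outcome. Section 3.6 schedules one follow-up visit, at 12 months.

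**The concern.** Censoring means that a patient contributes information up to the last date at which status is known, and no outcome is assumed after it. A logistic model or a chi-square test on a 12-month yes/no outcome has no such state, because every patient is a 0, a 1 or missing. A patient who leaves event-free before 12 months must therefore be coded 0 or left out, and neither is what Section 3.1 prescribes.

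The protocol fixes both the rule and the model, so this is more than detail left to a statistical analysis plan. For goal d, a later plan could honour Section 3.1 only by weighting the logistic model or replacing it.

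At stake is the goal d odds ratio. If leaving differs between patients with and without hyperkalaemia, which is plausible when one group is sicker, the choice between the two codings changes the estimate, and that choice is left open.

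**Working it through.** **1. The plan's own figures (Section 3.2).** Inputs: risks of 10% and 2.5%, a 7:1 ratio, 80% power and 95% confidence (two-sided assumed).

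- Pooled risk: (0.10 + 7 × 0.025)/8 = 0.0344.
- n exposed = [1.96 × √(0.0344 × 0.9656 × 8/7) + 0.842 × √(0.10 × 0.90 + 0.025 × 0.975/7)]² / 0.075² = 72.6, rounded up to 73; 7 × 73 = 511. This matches "73 exposed and 511 non-exposed patients should be included to have a 80% power".
- Incidence precision: 600 × 0.90 = 540 patients free of hyperkalaemia at baseline; 1.96 × √(0.05 × 0.95/540) = 1.84%, matching the stated ±1,8%.

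There is no arithmetic error. Both formulas use fixed binomial denominators with no censoring, so the precision figure treats cumulative incidence as a simple proportion.

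**2. Goal d odds ratio.** The planned value is (0.10/0.90)/(0.025/0.975) = 4.33.

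The protocol gives no leaving rate. For illustration, assume that 25% of exposed and 5% of non-exposed patients leave, evenly over the year, that leaving is unrelated to outcome within each group, and that events are spread evenly. About half of the leavers' events then fall before they leave.

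- Events observed, exposed: 10% × (1 − 0.25 × 0.5) = 8.75%.
- Events observed, non-exposed: 2.5% × (1 − 0.05 × 0.5) = 2.44%.
- Event-free completers, exposed: 0.75 × 90% = 67.5%.
- Event-free completers, non-exposed: 0.95 × 97.5% = 92.6%.

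| Handling of leavers | Odds, exposed | Odds, non-exposed | Odds ratio |
|---|---|---|---|
| Event-free leavers coded as event-free | 8.75/91.25 = 0.0959 | 2.44/97.56 = 0.0250 | 3.84 |
| All leavers dropped, including those with events | 10/90 = 0.1111 | 2.5/97.5 = 0.0256 | 4.33 |
| Event-free leavers dropped, earlier events kept | 8.75/67.5 = 0.1296 | 2.44/92.6 = 0.0263 | 4.93 |

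**3. Dependence on differential leaving.** With 10% leaving in both groups, the observed events are 9.5% and 2.375%.

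- Coded as event-free: (9.5/90.5)/(2.375/97.625) = 4.31.
- Event-free leavers dropped, earlier events kept: (9.5/81)/(2.375/87.75) = 4.33.

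The odds ratio hardly moves, so the effect in step 2 comes from the assumed difference in leaving.

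**4. Incidence, if it were computed as a simple proportion.** Take a true 5% and 10% leaving evenly. Coding leavers as event-free gives 5% × (1 − 0.10 × 0.5) = 4.75%. Dropping event-free leavers but keeping earlier events gives 4.75/(4.75 + 0.90 × 95) = 5.26%. For 5% to 20% leaving, the same formulas give 4.9% to 4.5% and 5.1% to 5.6%. These shifts of at most about 0.6 points lie within the ±1,8% precision.

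**The case against.** The strongest reply is that this is under-specification and not a strict conflict. A logistic model weighted for censoring is still a logistic model, so Sections 3.1 and 6 can both be honoured. That stands as far as it goes, but the protocol mentions no weighting, and the model as written cannot carry out the rule.

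Outcome data may also be recovered for patients who miss the final visit. Section 3.4 allows review of medical records, Section 3.5 has all available potassium values reviewed, and Section 3.6 collects hospitalisations since inclusion and death dates where possible. This may reduce the number truly lost. It supplies no analysis rule for those who remain.

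A reader might infer more than the text supports in four ways.

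- *The 12-month results are biased.* No leaving rate is given and none of the illustrative rates comes from the protocol. One of the three codings leaves the odds ratio unchanged.
- *Simple proportions are fixed for the incidences.* Section 6 names a quantity that a censoring-aware estimator delivers. Only the precision formula in Section 3.2 implies a proportion, and the estimator may properly be left to a statistical analysis plan.
- *The small margin between 584 and 600 is part of this problem.* Allowance for dropout in the sample size is a separate question.
- *Excluding patients who withdraw consent is an error.* The rule that they "retire their consent (and will be excluded from the analysis" can be a deliberate privacy choice. Whether data collected earlier may be kept depends on the consent form (Appendix 3), which is not shown.

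**Conclusion.** The point holds for the association analysis. Section 3.1 prescribes censoring, and the unweighted logistic regression and chi-square tests in Section 6 cannot apply it. The goal d odds ratio is at risk of bias of unknown size and direction. Under one assumed pattern (25% of exposed and 5% of non-exposed leaving evenly, unrelated to outcome within group), it ranges from 3.84 to 4.93 around a planned 4.33. With equal leaving there is next to no shift. Leaving that is related to outcome within groups would add bias that these figures do not cover.

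For the cumulative incidences there is no contradiction, only an unnamed estimator beside a precision figure computed as for a simple proportion. The change is worth making before analysis because it is cheap and concerns a stated objective. The documents do not show that any result will be wrong.

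**What to change.** Make Section 6 agree with Section 3.1:

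- Record for each patient the last date on which status is known.
- Estimate 12-month risks with censoring-aware methods: Kaplan-Meier for death and for the composite, and a cumulative incidence function with death as a competing event for hyperkalaemia and for admissions.
- Analyse the association by time-to-event regression with hyperkalaemia during follow-up as a time-varying exposure. If it were entered as a fixed covariate, the time before the first episode would be credited to the exposed group (immortal-time bias).
- Alternatively, keep the logistic model and weight it for censoring. Weighting deals with the leavers but not with the timing of the exposure, so the plan should then also say how exposure is classified in time.

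The cost is one extra date field and somewhat more analysis work. Section 3.6 already asks for death dates where possible, and Section 7 lists hospitalisation dates for serious adverse events. The time-varying analysis also needs the date of each hyperkalaemic value, which the case report form (Appendix 1, not shown) may already hold.
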